5.2.8 Phase 2: Cycle 7 and 10 Day 1 ( $\pm 1$  week)

If a patient remains on study drug beyond 4 cycles, he/she will only be required to return to the clinic every 3 months.

- Directed physical examination including weight and spleen size by palpation;
- Spleen size measurement by MRI (CT scan for patients not able to tolerate MRI). Imaging will be transmitted to a central imaging center for central reading;
- Vital signs (blood pressure, pulse, respiratory rate, and temperature);
- Laboratory tests (hematology, serum chemistries, and urinalysis, as listed in Appendix G);
- ECG – triplicate (pre-dose only; locally read);
- Bone marrow assessment, Cycle 7 only;
- Response assessment (IWG-MRT and ELN);
- JAK2 V617F allele burden if mutation present prior to start of therapy (pre-dose);
- MPN SAF (MPN-10) (pre-dose);
- Review patient study drug dosing diary for compliance and distribute study drug, Cycle 7 only;

- Assessment of AEs using the NCI CTEP CTCAE, version 4.0 (published 28 May 2009) (see Appendix H); and
- Concomitant medication notation.

5.2.9 Phase 2: Cycle 8, 9, 11 and 12 Day 1 ( $\pm 3$  days)

- Hematology and serum chemistry are to be obtained at the referring/local doctor's office and faxed to the study site, unless the patient is scheduled for a site visit.

5.2.10 Phase 2: Cycle 13, Day 1 and Day 1 of every 3 cycles thereafter ( $\pm 1$  week)

- Directed physical examination including weight and spleen size by palpation;
- Spleen size measurement by MRI (CT scan for patients not able to tolerate MRI). Cycle 13 and after completion of months 18 and 24 treatment cycles (i.e. Cycle 19 and 25). Imaging will be transmitted to a central imaging center for central reading; After 24 treatment cycles, MRI will be performed as clinically indicated; however is not required to be transmitted to a central imaging center for central reading.
- Vital signs (blood pressure, pulse, respiratory rate, and temperature);
- Laboratory tests (hematology, serum chemistries, and urinalysis, as listed in Appendix G);
- ECG – single reading (pre-dose only; locally read);
- Bone marrow assessment (pre-dose) Cycle 13 only, then annually;
- Response assessment (IWG-MRT and ELN);
- JAK2 V617F allele burden if mutation present prior to start of therapy (pre-dose);
- MPN SAF (MPN-10) (pre-dose);
- Assessment of AEs using the NCI CTEP CTCAE, version 4.0 (published 28 May 2009) (see Appendix H); and
- Concomitant medication notation.

5.2.11 Phase 2: End of Study Assessments

The following procedures will be performed within 30 days after the last dose of study drug or within 30 days after withdrawal from the study:

- Complete physical examination including weight and spleen size by palpation;
- Spleen size measurement by MRI (CT scan for patients not able to tolerate MRI) if not done within the past 8 weeks.
- Vital signs (blood pressure, pulse, respiratory rate, and temperature);
- ECOG Performance Status;
- Laboratory tests (hematology, serum chemistries, and urinalysis, as listed in Appendix G);
- ECG – triplicate or single reading if Cycle 13 or thereafter (locally read);
- Response assessment (IWG-MRT and ELN);
- MPN SAF (MPN-10);

- Collect any unused study drug and review patient study drug dosing diary for compliance, if applicable;
- Assessment of AEs using the NCI CTEP CTCAE, version 4.0 (published 28 May 2009) (see Appendix H); and
- Concomitant medication notation.

All efforts will be made to complete the end of study visit for early termination patients however review of laboratory tests obtained from referring/local doctor's office and a follow-up phone call to the patient may take place at a minimum for those patients refusing to return to the study site.

**5.2.12 Phase 2: Follow-up**

If an unresolved AE was observed at end of study visit, patients must be followed until the event resolves, until the event is judged stable and not expected to resolve completely, or until the patient begins alternative treatment.

**6 TREATMENT AND RESTRICTIONS**

**6.1 Treatment**

**6.1.1 Treatment Regimen, Dosage, and Duration**

Patients will be treated at the dose cohort level to which they are assigned. All study drug will be self-administered orally. NS-018 will be self-administered 2 hours or more after the last meal and at least 1 hour before the next meal.

The dose levels planned and the numbers of patients in each dose level are presented below.

Once Daily (QD) Cohort [completed]			Twice Daily (BID) Cohort							
Cohort	NS-018 Total Daily Dose(mg)	No. of Patients Per Cohort	Cohort	NS-018 Total Daily Dose(mg)	No. of Patients Per Cohort					
Phase 1			Phase 1							
QD 1#	75	3-6								
QD 2#	125	3-6								
QD 3#	200	3-6	BID 1#	200 (100×2) £	3-6					
QD 4#	300	3-6		—	—					
	—	—	BID 2#	400 (200×2) £	3-6					
	—	—	BID 3#	600 (300×2) £	3-6					
	—	—	BID 4#§	800 (400×2) £	3-6					
Phase 2	MTD or lower Up to 20 patients									
MTD = maximum tolerated dose.										
£ BID dosing must be administered 12 hours apart										
# If a DLT is experienced at any dose level, an intermediate cohort at a lower dose may be considered, as recommended by Safety Review Committee										
§ Additional cohorts at doses > 400 mg BID (800 mg/day) may be considered by the Sponsor if agreed by the Safety Review Committee after review of PK, PD, and safety data. The maximum planned increase in dose between cohorts will be 200 mg as the total daily dose (e.g., the dose level above 400 mg BID will not exceed 500 mg BID )										

During the study, a Safety Review Committee will review data from each cohort and may make dosing schedule changes based on the data review. The Safety Review Committee is described in detail in Section 13.9.

In the Phase 1 portion of the study, sequential cohorts of 3 to 6 patients will be treated with escalating doses until the MTD is established (see Section 6.1.1.3). The first patient in each cohort must be observed for at least 7 days of dosing with NS-018. If there is no clinically significant toxicity observed in that patient, enrollment in the cohort may continue. If a significant toxicity occurs, including any possible dose-limiting toxicity (DLT, see Section 6.1.1.2), the Safety Review Committee must meet and determine whether additional patients may be entered at that dose or an intermediate cohort at a lower dose should be considered. Each cohort can be assessed after at least 3 patients have completed 28 days of study drug dosing.

The Safety Review Committee can make dosing schedule changes (twice daily dosing rather than once daily dosing; intermediate dose levels if toxicity occurs that does not rise to the level of a DLT) based on pharmacodynamic, pharmacokinetic, and safety review. If twice daily dosing requires evaluation, dosing would start at one total daily dose level below the last once per day dose level that was declared safe. For example, when 300 mg QD was declared safe,

the starting dose for BID dosing would be 100 mg twice daily, 12 hours apart [representing a total daily dose 200 mg]).

Should BID dosing commence during the Phase I portion of the study, the SRC will meet after the last patient in that cohort has completed 28 days of dosing to assess the safety of that dosing schedule. Should the BID cohort be declared safe, the next BID cohort may begin. However, during the Phase 1 escalation portion of study, intrapatient schedule changes are not permitted (i.e., patients who start QD dosing regimen must remain on QD dosing and patients who start on BID dosing must remain on BID dosing).

If DLTs are seen in the 75 mg cohort, a cohort, labeled -1 and dosed at 50 mg, may be considered by the Safety Review Committee. Cohorts at doses >400 mg BID(800 mg/day) may be considered by the Sponsor if agreed by the Safety Review Committee after review of PK, PD, and safety data. The maximum planned increase in dose between cohorts will be 200 mg as the total daily dose (e.g., the dose level above 400 mg BID will not exceed 500 mg BID).

Once a cohort is declared safe, patients treated at lower doses in earlier cohorts can be considered for intrapatient dose escalation. Intrapatient dose escalation is permissible in individual patients if the patient has received at least 3 months of study drug at a given dose and has not experienced any Grade 3 or 4 drug-related toxicity and no evidence of significant clinical efficacy and the next highest dose cohort has already been declared safe by the Safety Review Committee. Intrapatient dose escalation depends on the total daily dose and the confirmation of safety based on QD and/or BID dose regimen at a dose level. For example a patient at 100mg BID can increase by up to 200 mg BID only when 200 mg BID is declared safe by the Safety Review Committee. In the event that intrapatient dose escalation would result in a patient escalating more than one dose at a time, the eligibility of the patient for dose escalation would be reviewed and the dose level determined by the investigator and the medical monitor.

After intrapatient dose escalation, patients will return to the study site after 1 month of treatment at the higher dose to undergo physical examination (including assessment of spleen size by palpation) and safety laboratory tests (hematology and chemistry). Patients will return to 3-month visit schedule after this visit.

When the MTD is reached, the Phase 2 portion of the study will commence. Additional patients will be added at the MTD level to confirm tolerability and explore efficacy, for a total of 20 patients. Consideration by the Safety Review Committee will also be given to suspending Phase 2 enrollment at the MTD, and instead adding the same total number of patients at a second dose level, the CAD. The CAD is defined as a dose level below the MTD with a clinically significant response rate and an acceptable toxicity profile as determined by the

investigator/medical monitor and sponsor. The expansion cohorts for the MTD and CAD, should they both be pursued, will not be concurrently open for enrollment. The two dose levels would instead be expanded sequentially. Consideration will also be given to enroll patients only at the CAD but not MTD level, based on the risk/benefit of therapy as judged by the investigator/medical monitor and sponsor. After Phase 2 has started, patients who are continuing treatment from the Phase 1 portion of the study are able to change to the Phase 2 dose as intrapatient dose escalation, and based on risk/benefit as judged by the investigator. A change of schedule is allowed, such as a change from a QD Phase 1 dose to a BID Phase 2 dose. Since a patient could potentially be escalated by more than one dose upon crossing over from Phase 1 to the Phase 2 dosing schedule, the eligibility of the patient for dose escalation would be reviewed and the dose level determined by the investigator and the medical monitor. A patient must receive at least 3 months of study drug at the Phase 1 dose and not experience any Grade 3 or 4 drug-related toxicity before being escalated to the Phase 2 dosing schedule.

During the Phase 2 portion of the study, the Safety Review Committee will meet when a DLT-equivalent AE occurs, in order to determine whether additional patients may be enrolled at the same dose level or at a lower dose thereafter. In addition, the Safety Review Committee will meet when the number of patients completing Cycle 1 reaches 10 to review the pooled safety information to determine if further enrollment is warranted. Any DLTs that occur at a dosing schedule will be evaluated separately.

#### 6.1.1.1 Dose Reductions/Delays

Patients who experience a DLT, as defined in Section 6.1.1.2, **must** have study drug administration interrupted: 1) when a Grade 4 drug related toxicity returns to  $\leq$ Grade 1 or to baseline within 4 weeks of study drug interruption, the investigator may recommence treatment, but at one dose level below that at which the toxicity occurred; 2) when a Grade 3 drug related toxicity returns to  $\leq$ Grade 1 or to baseline within 4 weeks of study drug interruption, the investigator may recommence treatment at one dose level below that at which the toxicity occurred, or after discussion with the medical monitor, at the same dose at which the toxicity occurred. Discussion on the appropriateness of the patient continuing in the study will also include an evaluation of the current clinical response.

At each step, the investigator must carefully evaluate the relevant risks and benefits to the patient of continued study participation. A second dose reduction can be considered by the investigator if a second significant toxicity occurs, to one further cohort dose below. Patients whose baseline dose has been reduced for toxicity cannot be dose escalated back to the prior dose.

Study drug administration may be interrupted for clinically significant toxicities of  $\geq$ Grade 1 that do not meet DLT criteria, at the discretion of the investigator. Once the toxicity has resolved to Grade 0 or 1, or to baseline level within 4 weeks of study drug interruption, study drug may be resumed at either the same dose or one dose level below, at the discretion of the investigator. Furthermore, subjects who experience Grade 4 life-threatening non-hematological toxicity will not be eligible for further treatment, unless reviewed by the Safety Review Committee and deemed appropriate for continued follow up and possible re-initiation of study drug.

Antidiarrheal or antiemetic therapy must be administered before interrupting therapy for Grade 1 or 2 nausea, vomiting, and/or diarrhea.

Patients whose dose is reduced will continue the regular schedule of assessments.

Patients requiring a  $>4$  week interruption in study drug administration should be withdrawn from the study, unless reviewed by the Safety Review Committee and deemed appropriate for continued follow up and possible re-initiation of study drug.

These guidelines for dose reductions or delays also apply to patients in Phase 2 who experience a drug related toxicity

#### 6.1.1.2 Definition of Dose-Limiting Toxicity

A DLT is defined as any one or more of the following events that is unrelated to underlying disease, intercurrent illness, or concomitant medications:

- Grade 4 neutropenia, thrombocytopenia, anemia, or lymphopenia
- Grade 3 or 4 hematologic toxicity other than the above
- Grade 3 or 4 non-hematologic toxicity,

For nausea, vomiting, and/or diarrhea to be considered a DLT, the event must persist for at least 72 hours despite the use of an optimal antiemetic or antidiarrheal regimen. The optimal antiemetic regimen is to be determined by each investigator and should at a minimum include a 5-HT3 antagonist. The optimal antidiarrheal regimen is to be determined by each investigator and should at a minimum include Imodium®(Loperamide hydrochloride) or Lomotil®(diphenoxylate hydrochloride and atropine sulfate). Grade 3 nausea, vomiting, and/or diarrhea will not be considered a DLT in patients who did not receive optimal treatment with antiemetics or antidiarrheals.

Important medical events other than those listed above may be considered a DLT based upon appropriate medical judgment and discussion by the Safety Review Committee (e.g., the same clinically significant toxicity not qualifying

as a DLT, but observed in multiple patients, or chronic Grade 2 toxicity that persists for more than 4 weeks despite interruption of therapy).

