#### 8.1.3.2 Intensity

Investigators should assess the severity of AEs according to CTCAE (see Appendix H). In general, CTCAE v4.0 Severity Grades are:

Grade 1:	Mild; asymptomatic or mild symptoms; clinical or diagnostic observations only; intervention not indicated;
Grade 2:	Moderate; minimal, local or noninvasive intervention indicated;
Grade 3:	Severe or medically significant but not immediately life-threatening; hospitalization or prolongation of hospitalization indicated; disabling; limiting self-care;
Grade 4:	Life-threatening consequences; urgent intervention indicated;
Grade 5:	Death related to AE.

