**12.5 Safety Analyses**

All safety analyses will be based on the Safety Population. Adverse events, vital sign measurements, clinical laboratory information, ECG measurements, and concomitant medications will be summarized by dose level.

Adverse events will be coded using the Medical Dictionary for Regulatory Activities (MedDRA) classification system. The severity of all AEs will be graded according to the NCI CTEP CTCAE version 4.0. A summary of all AEs will be provided by system organ class and preferred term. The same summaries will be performed for Grade 3/4 AEs and drug-related AEs. Listings will be presented for SAEs, Grade 3/4 AEs, and AEs leading to discontinuation from the study.

Clinical laboratory evaluations at each visit and change from baseline (Cycle 1 Day 1) will be summarized by dose level. A laboratory value shift table will be provided. Vital signs and ECG parameters at each assessment time will be summarized by dose level. Other safety variables and their changes from baseline (when applicable) will be summarized by dose level at each of the scheduled assessment times.

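### Severe-event outputs and dose-limiting toxicity (DLT) categories stop at Grade 4, though the protocol's severity scale has a separate Grade 5 for fatal events

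*Combined protocol and SAP*

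**What the plan says.** **Severity scale.** Section 8.1.3.2 sets out the CTCAE v4.0 grades. Grade 4 is the life-threatening level. Grade 5 is a level of its own, "Death related to AE".

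**DLT definition.** Section 6.1.1.2 lists three categories for events not explained by disease, intercurrent illness or concomitant medication:
- "Grade 4 neutropenia, thrombocytopenia, anemia, or lymphopenia"
- "Grade 3 or 4 hematologic toxicity other than the above"
- "Grade 3 or 4 non-hematologic toxicity"

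A closing clause adds: "Important medical events other than those listed above may be considered a DLT based upon appropriate medical judgment", following discussion by the Safety Review Committee.

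**Safety outputs.** Section 12.5 starts with an output that has no grade limit: "A summary of all AEs will be provided by system organ class and preferred term". It continues: "The same summaries will be performed for Grade 3/4 AEs and drug-related AEs". On listings it says: "Listings will be presented for SAEs, Grade 3/4 AEs, and AEs leading to discontinuation from the study". It names no output for Grade 5, for Grade 3 or higher, or for deaths.

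**The concern.** Safety is a primary objective of both phases. The Grade 3/4 summary is the only table planned in Section 12.5 that is restricted by severity, so readers will take the severe-event rate from it. As worded, that table leaves out the worst grade on the protocol's own scale.

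The same wording appears in the DLT categories. The rules table in Section 6.1.1.3 acts on the number of patients with a DLT. A qualifying Grade 3 non-hematologic event enters that number by definition. A fatal event unrelated to the listed exceptions enters it only through a clause that says it may be considered. In Phase 2, Sections 6.1.1 and 13.9 call a committee meeting when a DLT-equivalent event occurs, so the unclear status of Grade 5 carries over to that trigger.

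**Working it through.** No figure in the plan depends on this point, so there is none to reproduce. The check compares the sections and then does one short calculation.

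**Step 1: does Grade 3 or 4 include Grade 5?** In Section 8.1.3.2, Grades 4 and 5 are separate levels. None of the three DLT categories names Grade 5 or death, and none is worded as a grade or higher. Section 6.1.1.1 does use an at-or-above form (Grade 1 and above) for treatment interruptions, so the authors used open-ended wording where they wanted it. Grade 5 is therefore in 0 of the 3 listed categories.

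**Step 2: where does a Grade 5 event appear under Section 12.5?**

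| Output | Contains an event recorded only as Grade 5? |
|---|---|
| Summary of all AEs | Yes, no grade limit |
| Summary of drug-related AEs | Yes, if judged related |
| Summary of Grade 3/4 AEs | No |
| Listing of SAEs | Yes, because death is a seriousness criterion in Section 8.1.3.1 |
| Listing of Grade 3/4 AEs | No |
| Listing of AEs leading to discontinuation | Not stated |
| Deaths table or listing | None named |

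**Step 3: size in the severe-AE rate.** Let n be the number of patients at a dose level, and k the number whose only Grade 3 or higher event is Grade 5.
- Rate as planned = (patients with at least one Grade 3 or 4 event) / n
- Rate including Grade 5 = (patients with at least one Grade 3, 4 or 5 event) / n
- Difference = k / n

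The Phase 2 sample size in Section 12.1 is 20. With all 20 at one dose level and k = 1, the difference is 1/20 = 0.05, or 5 percentage points per such patient. The dose table in Section 6.1.1 says up to 20, and Section 12.5 summarises by dose level. With fewer patients at a level, the step is larger, at 100/n points.

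A patient who also has a separate Grade 3 or 4 record adds nothing to k and stays in the overall rate. In the rows by preferred term, however, the fatal term itself is still missing unless that term also has a Grade 3 or 4 record. The documents do not say whether an event that worsens from Grade 4 to Grade 5 is kept as one record or two.

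**Step 4: DLT status.** No numerical size can be derived. It would depend on how often the committee declined to class a drug-related death as a DLT, and the documents give no basis for such a rate.

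**The case against.** The strongest reply is that no death would be overlooked. Section 12.5 carries a fatal event in the all-AE summary and the SAE listing, and in the drug-related summary if it is judged related. Section 8.2 requires SAEs to be reported within 24 hours. A reader might infer from the Grade 3/4 wording that deaths go unreported. The documents do not support that, because each of these routes captures them.

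A second tempting inference is that a death would automatically turn 1/3 into 0/3 and trigger escalation, or turn 2/6 into 1/6 and make a dose look tolerable. The documents do not support that either. Section 6.1.1.2 lets the committee class such an event as a DLT, and Section 13.9 requires the committee to review each cohort before the next one opens. It must also meet if clinically significant toxicity occurs in a cohort's first patient during the first 7 days. In Phase 2 it reviews pooled safety once 10 patients have completed Cycle 1. A miscount would require the committee to examine such a death and decline to count it.

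Third, Section 12 defers detail to a Statistical Analysis Plan. The text available contains the protocol's statistics section but no separate table list, so a deaths table may be planned elsewhere.

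These points limit the consequences and stand. They do not close the gap in wording. The severity-restricted summary and listing still exclude Grade 5 as written, and the DLT definition still does not say how Grade 5 is treated.

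**Conclusion.** The point holds as an inconsistency between Section 8.1.3.2 on one side and Sections 6.1.1.2 and 12.5 on the other. The most likely intention is Grade 3 or higher, but the text does not say so.

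- **Reporting.** An event recorded only as Grade 5 is absent from the one severity-restricted AE summary and its listing. The effect on the overall severe-AE rate is 5 percentage points per affected patient. This assumes 20 Phase 2 patients at one dose level, and that the patient has no other Grade 3 or 4 record. It would be wrong to infer that every death lowers the rate by 5 points.
- **DLT definition.** A Grade 5 event counts by committee discretion, whereas lesser listed events count by rule. This is a gap in the definition with no numerical size. It does not show that a death cannot be a DLT or that escalation would follow one.

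The correction is worth making because safety is a primary objective and the change is small.

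**What to change.** **Section 12.5.** Change the summary and the listing from Grade 3/4 to Grade 3 or higher, and add a deaths table and listing. State which deaths these cover, since Section 8.1.2 keeps disease progression out of the AE record.

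**Sections 6.1.1.2 and 8.1.3.2.** Reconcile them so that the protocol says explicitly how Grade 5 events are treated in the DLT definition. The choice of rule is left to the sponsor and the Safety Review Committee.

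**Cost.** New wording in two sections and a small additional deaths output, with no new data collection and no change in sample size. The reported severe-AE rate may be slightly higher than under the present wording.

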#### 6.1.2 Compliance Control

Patient compliance will be monitored by assessing the tablet count from the drug packages returned at each visit. Patients will complete a study drug dosing diary daily that will document the time of day they took their study drug. Tablet counts will be compared by the site to the dosing diary to further assess compliance and aid patient education regarding compliance. Documentation on the electronic Case Report Form (eCRF) will account for patient compliance during each cohort. Patients will be instructed to return any unused study drug and packaging when attending clinic visits or if the patient is discontinued before the study is complete.

Patients who take  $<80\%$  of the expected prescribed regimen will be counseled on the importance of taking the study drug appropriately. If compliance is  $<80\%$  during the first month of therapy, the patient will be counseled, remain on study drug and will follow the study assessment schedule. The patient will be included in all final study analysis populations (See Section 12.2), however the patient will not be included in the data from each cohort that is reviewed by the Safety Review Committee to determine dosing schedule changes. In the event that a patient's compliance is  $<80\%$  during the first month of therapy, an additional patient will be enrolled in the cohort and their data will be included in the cohort review by the Safety Review Committee as well as in all final study analysis populations.

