### **13.9 Safety Review Committee**

A Safety Review Committee, consisting of the actively recruiting investigators, the medical monitor overseeing the study for NS Pharma and a NS Pharma representative will meet to evaluate each cohort. If clinically significant toxicity occurs in the first patient in any cohort during their first 7 days of NS-018 dosing, the Safety Review Committee will meet and determine dosing for future patients. The Safety Review Committee must review each cohort before patients can be enrolled into the next cohort. The Safety Review Committee can make dosing schedule changes (twice daily dosing rather than once daily dosing; intermediate dose levels if toxicity occurs that does not rise to the level of a DLT) based on pharmacodynamic, pharmacokinetic, and safety review. If twice daily dosing requires evaluation, dosing would start at one total daily dose level below the last once per day dose level that was declared safe.

If DLTs are seen in the 75 mg cohort, a cohort, labeled -1 and dosed at 50 mg, may be considered by the Safety Review Committee. Cohorts at doses >400 mg BID(800 mg/day)may be considered by the Sponsor if agreed by the Safety Review Committee after review of PD, PK, and safety data. The maximum planned increase in dose between cohorts will be 200 mg as the total daily dose (e.g., the dose level above 400 mg BID will not exceed 500 mg BID).

Should BID dosing commence during the Phase I portion of the study, the SRC will meet after the last patient in that cohort has completed 28 days of dosing to assess the safety of that dosing schedule. Should the BID cohort be declared safe, the next BID cohort may begin. BID cohorts and QD cohorts may enroll simultaneously provided the previous lower dose of each cohort type has been declared safe by the SRC.

During the Phase 2 portion of the study, the Safety Review Committee will meet when a DLT-equivalent AE occurs, in order to determine whether additional patients may be enrolled at the same dose level or at a lower dose thereafter. In addition, the Safety Review Committee will meet when the number of patients who have completed Cycle 1 reaches 10 to review the pooled safety information to determine if further enrollment is warranted.

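### In the Phase 1 BID cohorts, a patient whose lasting Grade 3 nausea, vomiting or diarrhea is discounted for lack of the minimum supportive regimen still counts as DLT-free in the 3+3 decision

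*Combined protocol and SAP*

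**What the plan says.** Section 6.1.1.2 makes Grade 3 or 4 non-hematologic toxicity a DLT. Nausea, vomiting and diarrhea carry an extra condition: they must last at least 72 hours despite an optimal regimen. The investigator chooses the antiemetic regimen, but it "should at a minimum include a 5-HT"₃ antagonist; the antidiarrheal regimen needs at least loperamide or diphenoxylate/atropine. The section then adds that "Grade 3 nausea, vomiting, and/or diarrhea will not be considered a DLT in patients who did not receive optimal treatment" with those drugs.

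Section 6.1.1 says of timing: "Each cohort can be assessed after at least 3 patients have completed 28 days of study drug dosing". It sets no condition on supportive treatment. Section 6.1.1.3 counts patients with a DLT: none of 3 escalates, 1 of 3 leads to up to 3 more patients, and 2 of 3 means the MTD is exceeded.

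Section 6.1.2 has the only stated rule that takes a patient out of the cohort decision and adds another. If first-month compliance is below 80%, that patient is left out of the data for the dosing decision and "an additional patient will be enrolled in the cohort and their data will be included in the cohort review". The synopsis speaks of evaluable patients without defining the term, and Section 12.2 has no DLT-evaluable population.

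Appendix E lists ondansetron among the prohibited CYP1A2 and CYP3A4 substrates. Section 6.2.1 allows antiemetics as supportive care.

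The dose table in Section 6.1.1 marks the once-daily cohorts as completed, so the rule now matters for the BID cohorts.

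**The concern.** The gastrointestinal clause tests whether the event persists despite proper treatment. In a patient who never received that treatment, the test was not applied. If the event went on for 72 hours or more, or stopped only because NS-018 was held or lowered, nobody can say whether the regimen would have controlled it. The result is missing, but the counting rule records it as negative.

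This patient can readily stay in the count. Under Section 6.1.1.1, after a toxicity that does not meet the DLT definition, the drug may be interrupted and then resumed at the same dose or one level lower, and the patient keeps the regular assessment schedule. Nothing removes the patient from the DLT count at the original dose.

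At stake is the escalation decision. A 3+3 cohort rests on three to six patients, so one missing result recorded as negative makes clearance easier and can push the MTD upward. The protocol expects these events: they have their own DLT clause, and Section 6.1.1.1 requires antiemetics or antidiarrheals before drug is interrupted even for Grade 1 or 2 events. For nausea and vomiting, the ban on ondansetron makes omission of the required class somewhat more likely.

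**Working it through.** **The plan's own figures.** The plan gives no figure on this point. Its only computed figures, the Section 12.1 table for 20 Phase 2 patients, follow from 1 − (1 − p)^20. They reproduce as 64.15, 87.84, 96.12, 98.85 and 99.92% at 5, 10, 15, 20 and 30%. They do not bear on the escalation rule.

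**Reading the rule.** Take two patients without toxicity and a third with Grade 3 vomiting for four days and no 5-HT3 antagonist.
- Section 6.1.1.2: the third patient has no DLT.
- Section 6.1.1: three patients have completed 28 days, so the cohort can be assessed.
- Section 6.1.2: compliance is at least 80%, so there is no replacement.
- Section 6.1.1.3: the cohort reads 0/3 and escalates.

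**Inputs.** The escalation rule is from Section 6.1.1.3, with all 3 additional patients entered after 1/3. The DLT rate p in informative patients is assumed at 20, 30 or 40%, because the documents give none. No Committee intervention is assumed.

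**One discounted patient among the first three.**
- Replaced, so three informative patients: Clear(p) = (1 − p)³ + 3p(1 − p)⁵.
- Counted as DLT-free, so two informative patients: (1 − p)² + 2p(1 − p)⁴.

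| p | Counted DLT-free | Replaced |
|---|---|---|
| 20% | 0.640 + 0.164 = 0.804 | 0.512 + 0.197 = 0.709 |
| 30% | 0.490 + 0.144 = 0.634 | 0.343 + 0.151 = 0.494 |
| 40% | 0.360 + 0.104 = 0.464 | 0.216 + 0.093 = 0.309 |

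If the other two are already known to be clean, the written rule escalates with certainty. With replacement, the probability is (1 − p) + p(1 − p)³: 0.902 at 20%, 0.7 + 0.3 × 0.343 = 0.803 at 30%, and 0.686 at 40%.

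**How much replacement recovers.** This is illustration only; every share is assumed. Let the true rate be t = 0.30, let half of DLTs be of the kind that can be discounted, and let 25% or 50% of those be discounted. The probability of a discounted true DLT is then m = 0.30 × 0.5 × 0.25 = 0.0375, or 0.30 × 0.5 × 0.50 = 0.075.
- All DLTs counted: Clear(0.30) = 0.494.
- Discounted patients counted as DLT-free, p = t − m = 0.2625 or 0.225: 0.573 or 0.654.
- Replaced, every discounted event a true DLT, p = (t − m)/(1 − m) = 0.2727 or 0.2432: 0.551 or 0.615.
- Replaced, half of the discounted events controllable, p = (t − m)/(1 − 2m) = 0.2838 or 0.2647: 0.528 or 0.568.

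Replacement therefore removes about a quarter of the excess in the first case (0.022 of 0.079, or 0.039 of 0.160) and a little over half in the second (0.045 of 0.079, or 0.086 of 0.160). The rest can be removed only by treating the event properly, so that it is not discounted.

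**The case against.** The best defense is that the clause is sound and the affected group small. The patient must have a Grade 3 event that lasts 72 hours or ends only on a dose change, must never receive the minimum regimen, must complete 28 days and must take at least 80% of doses. Starting the regimen after onset makes the event assessable again. The Section 6.1.1.3 table counts DLTs during study treatment, so a later event that is treated and persists would still count. All of this stands and limits the frequency.

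The Safety Review Committee is also a real check. Section 13.9 says: "The Safety Review Committee must review each cohort before patients can be enrolled into the next cohort". For significant toxicity in a cohort's first patient, Section 6.1.1 says "the Safety Review Committee must meet and determine whether additional patients may be entered at that dose" or consider a lower intermediate dose. The Committee may call other important events DLTs; one example given is "the same clinically significant toxicity not qualifying" as a DLT but seen in several patients. Meeting and reviewing are mandatory; reclassifying is not, and no provision asks for replacement. One discounted Grade 3 event in one patient is not among the examples.

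Four stronger readings are tempting, and the documents do not support them.
- *Every discounted patient is uninformative.* An event that resolved within 72 hours on unchanged dosing, without the regimen, gives no reason to think it would have lasted longer with it. That patient is reasonably DLT-free.
- *The protocol makes its own antiemetic regimen impossible.* Ondansetron is the only 5-HT3 antagonist that Appendix E names. The class is not banned, and another agent could satisfy both rules. Because the appendix refers to an outside website for further drugs, the text alone does not show which agent is safe to choose. Neither loperamide nor diphenoxylate/atropine appears in its tables.
- *The dog data place the problem at the top BID dose.* Section 1.2.1 reports vomiting and/or diarrhea after single doses of 20 mg/kg or more. By the protocol's conversion that is 20 × 27.8/50 × 60 = 667 mg at once, whereas the highest listed BID cohort takes 400 mg per dose.
- *Halving NS-018 under Section 6.2.1 is a second route.* It requires a patient who is benefiting, and the first scheduled response assessment is Cycle 2 Day 1, so it is remote in Cycle 1.

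**Conclusion.** The concern holds for Phase 1 BID cohorts and for a defined group: Grade 3 nausea, vomiting or diarrhea without the minimum regimen that lasted at least 72 hours or ended only after NS-018 was interrupted or reduced. Such a patient, with 28 days completed and compliance of at least 80%, is counted as DLT-free although the DLT status is unknown.

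The direction is firm: compared with replacement, the rule makes a cohort easier to clear. The size is not known. The 63% against 49% at an assumed 30% rate is conditional on one such patient among the first three and on no Committee action; the gap is 9 to 15 percentage points over assumed rates of 20 to 40%. A reader might infer that the MTD will be too high by some stated amount. The documents give no DLT rate, no gastrointestinal share and no discount share, so that does not follow.

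This is a design choice worth correcting, of minor to moderate priority.

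**What to change.** 1. In Sections 6.1.1.2 and 6.1.2, state that a Phase 1 patient is not DLT-evaluable at that dose if the patient had Grade 3 nausea, vomiting or diarrhea without the minimum regimen, the event lasted at least 72 hours or ended only after NS-018 was interrupted or reduced, and there was no other DLT. Replace the patient for the cohort decision through the existing Section 6.1.2 mechanism, and report the event to the Safety Review Committee. State also that a patient whose event resolved within 72 hours on unchanged dosing stays evaluable and DLT-free.
2. In Appendix E or Section 6.1.1.2, name a 5-HT3 antagonist that may be used without reducing NS-018. This prevents discounting of nausea and vomiting in the first place, which replacement alone cannot do.

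The cost is protocol wording, an occasional replacement patient, and up to about one more 28-day cycle for the cohort concerned. Patients remain in the final analysis populations, as they already do under Section 6.1.2.
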